# RESUME\_STUDY Clinical study EOXY BIOSERENITY\_80601-2-61

Title	Clinical Trial testing the BioSerenity Pulse Oximeter (EOXY) efficacy, performance and safety in healthy volunteer
NCT	NCT03614416
Document date	05 june 2017

Objectives Primary objective: evaluate the SpO2 and HR accuracy of the Bioserenity	
Primary objective: evaluate the SpO2 and HR accuracy of the Bioserenity pulse oximeter (EOXY), evaluating the performance of the device compared to invasive method blood sampling (SaO2) by CO-Oximeter, and compared to a pulse oximeter gold standard.	
Secondary objective 1: measurement of the variation of the fraction of inspired oxygen (FiO2).	
Secondary objective 2: validation of the algorithm for data review and analysis of signal.	
Type: Wireless non-invasive and reflectance-based pulse oximeter developed by Bioserenity	
Description: As opposed to transmittance oximeters, the photodiodes of reflectance-based oximeters collect the light emitted by the LEDs and reflected (as opposed to crossing light) by the bones, tissues and muscles. The reflectance type pulse oximeters can perform measurement from various sites of the body, excluding the limitation of measurement position [1].	
Using of the device for the study: Intended to be used to acquire and transmit recorded data from adults. The EOXY permits non-invasive, continuous acquisition and monitoring of the pulse rate (PR) and of the oxygen saturation level in the blood (SpO2) of adults. For the study, it is intended to be used on different body site as the forehead, the chest or the back.	

Abstract\_EOXY Page 1 on 4

### RESUME\_STUDY Clinical study EOXY BIOSERENITY 80601-2-61

#### Method

According to the European standard ISO 80601-2-61:2011, clinical investigation is conducted in order to assess the performance and safety of pulse oximeters, comparing the measured EOXY SpO2 values to SaO2 values collected by invasive methods using blood sampling, and comparing the EOXY heart rate values to goldstandard heart rate.

The EOXY SPO2 and HR measurements, is performed in O2 saturation conditions up to 100% and then in different desaturation plateaus, ranging from 100 % to 70%. Three EOXY pulse oximeters record the SpO2 and HR at the same time in 3 different body areas: chest, back-torso, forehead. Different body areas are tested in order to assess separately the safety and performance of the EOXY device on these areas. The EOXY SpO2 values is simultaneously compared to SaO2 measures providing from invasive blood sampling taken from an indwelling arterial catheter. The EOXY heart rate measures is compared to a gold standard oximeter CE-marked. The controlled desaturation is performed in five progressive plateaus from 100% to 70%. As the example given in the ISO standard, we choose to do the test on the 70-100% desaturation range, with 5 plateaus (100%-97%; 97%-92%; 92%-85%; 84%-78%; 77%-70%). 5 SPO2 values, 5 SaO2 values (blood samples) and 5 heart rate measures are collected per plateau, for each of 13 subjects.

The desaturation plateaus are reached using controlled FiO2 levels performed by a device. It permits to bring subjects near target levels of desaturation plateaus and to maintain them at the target plateau during the 5 blood samples.

A number of inclusions of 13 was chosen to have at least 10 subjects, in case of drop-outs or analysis exclusions. ISO 80601-2-61:2011 standard advices to collect 200 pairs of data.

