#### RESUME\_STUDY Clinical study EOXY BIOSERENITY\_80601-2-61

	7
	Exclusion criteria: - Smokers or individuals exposed to high levels of carbon monoxide that result in elevation of carboxy hemoglobin levels
	- Individual subject to conditions that result in elevated levels of methemoglobin
	- Subject who would be placed at undue medical risk associated with any procedure called for in the protocol
	- Subject with open wounds
	- Pregnant woman (negative pregnancy test needed)
	- Subject allergic to silicon, polyamide and silver yarn
	- Subject with cardiorespiratory disorders likely to worsen with thoracic pressure applied by the textile band
	- Subject with mental or motor impairment preventing him from expressing pain
	- Subject with blood or skin disorder that may impacting results
	- Subject with behavioral disorders, too agitated or too aggressive
	- Subject with sensorial disorders, insensible to skin pain
	- Subject susceptible to tension/pressure-based headaches
	No vulnerable subject is enrolled on this study.
Duration of participation and follow-up	Participation duration: 2 days (3 days for subjects of phase 1) No follow-up visit planned
End point criteria	Primary objective: -For performance: Collection of 5 different values of SpO2, SaO2 and HR after each desaturation plateau. These values are used for the analysis of the performance of the EOXY device and the performance of the gold standard, following the ISO 80601-2-61:2011 standardFor safety: Monitoring of vital sign: heart rate ( HR ) continuously, blood pressure and temperature between each desaturation plateau. Also, adverse events are collected during the study.
	Secondary objective 1: FiO2 is assessed to bring subjects near target levels of desaturation plateau. No analysis is performed on these data.
	Secondary objective 2 : Assessment thanks to the signal analysis. No data analysis performed
Statistical method	The clinical performance analysis for this study is assessed by the Accuracy Root-Mean square (ARMs) (calculated by the difference between the investigational pulse oximeter SpO2 measurement and the co-oximeter's SaO2 measurements) and is assessed by the Bland-Altman plot visualizing the difference between SpO2 and SaO2.

Abstract\_EOXY Page 3 on 4

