# RESUME\_STUDY Clinical study EOXY BIOSERENITY\_80601-2-61

	ARMS is a representation of the combination of systematic and random error. It is defined as the accuracy root-mean-square error difference between the measured value and the truth value calculated as below, where "n" is the number of observations, and both SpO2 and SaO2 are defined as:
Safety assessment	Assessment of the number of undesirable effects
References	[1] Marcus Kramer, Aaron Lobbestael et al. Wearable Pulse Oximetry Measurements on the Torso, Arms, and Legs: A Proof of Concept; Military medicine 182(S1):92-98 · March 2017

Abstract\_EOXY Page 4 on 4

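### Does counting five SpO2 values per plateau, without saying per body site, leave each site short of the 200 pairs cited?

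*Combined protocol and SAP*

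**What the plan says.** The document is a four-page abstract, and the point rests on a few statements in it.

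- **Method, recording.** "Three EOXY pulse oximeters record the SpO2 and HR at the same time in 3 different body areas: chest, back-torso, forehead".
- **Method, purpose.** "Different body areas are tested in order to assess separately the safety and performance of the EOXY device on these areas".
- **Method, count.** "5 SPO2 values, 5 SaO2 values (blood samples) and 5 heart rate measures are collected per plateau, for each of 13 subjects". There are five plateaus.
- **Method, size.** Thirteen subjects are enrolled so that at least 10 remain, and "ISO 80601-2-61:2011 standard advices to collect 200 pairs of data". No other basis for the sample size is given.
- **End point criteria.** The count is repeated without a site: "Collection of 5 different values of SpO2, SaO2 and HR after each desaturation plateau".
- **Statistical method.** Accuracy is judged by ARMS and a Bland-Altman plot of SpO2 against SaO2. In the ARMS definition, n "is the number of observations, and both SpO2 and SaO2 are defined as"; the equation that follows is not reproduced in the text available.
- **Safety assessment.** "Assessment of the number of undesirable effects", with no site named.

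**The concern.** Three units read at each of five blood samples produce 15 EOXY SpO2 values per plateau and subject, and 15 EOXY heart rate values. The plan says five of each. A strict reader could take five as everything collected from the subject at that plateau, to be shared among three sites.

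This would matter because the plan wants a separate answer for each site and its only size argument is the 200 pairs. The two readings of five fall on opposite sides of 200, both with 10 subjects and with all 13. The endpoint, statistical and safety rows do not settle the point, since none of them mentions a site. On the less favourable reading, the plan would promise three separate accuracy assessments and supply too few pairs for at least two of them.

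**Working it through.** **Inputs.** From the Method section: 5 plateaus; 5 values per plateau and subject; 3 units at 3 sites; 13 subjects enrolled and at least 10 evaluable; 200 pairs cited. The plan states no planned total of pairs, so there is no figure of its own to reproduce.

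**Blood samples.** 5 × 5 = 25 per subject, so 25 × 10 = 250 with 10 subjects and 25 × 13 = 325 with 13.

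**Reading A: five per site.** Every blood sample is paired with all three units.

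- Pairs per site: 250 (10 subjects) or 325 (13 subjects).
- Pairs over three sites: 3 × 250 = 750 or 3 × 325 = 975.
- Complete subjects needed for 200 pairs at a site: 200 / 25 = 8.
- Pairs that can be lost before a site falls below 200: 1 − 200/250 = 20.0% with 10 subjects; 1 − 200/325 = 38.5% with 13.

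**Reading B: five in total over sites.** An equal split is assumed; the plan gives none.

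- Pairs per site: 250 / 3 = 83.3 or 325 / 3 = 108.3.
- Complete subjects needed for 200 pairs at a site: 200 / (25/3) = 24.
- With an unequal split, one site could still reach 200, but two could not, because 2 × 200 = 400 exceeds 325.
- Pairs over the whole study: 250 or 325, both above 200.

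**Which reading fits the design?** Three features of the Method section bear on this.

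1. The units record at the same time, and the SpO2 values are compared with the simultaneous arterial samples. At each sample all three units therefore have a value to pair. Reading B would leave most of those values unused.
2. The count lists SpO2, SaO2 and heart rate as matching fives. SaO2 belongs to the subject and not to a site, so five describes sampling moments.
3. Five does not divide by three. Reading B would need an allocation rule within each plateau, and the plan has none.

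All three point to reading A.

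**What would reading B cost in precision?** Take zero-mean normal errors and let r be the subject's share of the error variance, assumed to lie between 0.2 and 0.5. With N subjects and m pairs per subject and site, the relative standard error of a site's ARMS is

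0.5 × √( 2 × (1 + (m − 1) × r²) / (N × m) ).

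For example, N = 10, m = 25 and r = 0.5 give 0.5 × √(2 × 7 / 250) = 11.8%.

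| m | r | N = 10 | N = 13 |
|---|---|---|---|
| 25 (A) | 0.2 | 6.3% | 5.5% |
| 25 (A) | 0.5 | 11.8% | 10.4% |
| 25/3 (B) | 0.2 | 8.8% | 7.7% |
| 25/3 (B) | 0.5 | 13.0% | 11.4% |

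The largest gap between the readings is 2.5 percentage points (8.8 against 6.3). The gap is limited because pairs from one subject are correlated, so tripling them adds less information than the raw count suggests.

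**The case for a change.** The best case for a change accepts reading A and argues that two gaps remain. First, the plan does not say whether 200 applies to each site or to the study. If it is a study total, 750 to 975 pairs meet it easily, and one site could lose many pairs unnoticed; with 10 subjects, losing more than 20% of a site's pairs takes it below 200. Second, n in ARMS is not tied to a site, so the text read alone would permit a single ARMS over all three sites.

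The first gap is real as a matter of wording. But the documents do not show that 200 was ever a requirement for each site, and writing that in would add a condition they do not state. The second gap has less force. The Method section commits to assessing the areas separately, and one pooled figure would contradict it. The missing equation may also have carried a site index, so its absence here is weak evidence.

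It is also fair to the concern that its shortfall does not depend wholly on an equal split: under reading B at least two sites would miss 200 however the values were divided. That still requires reading B to be right and 200 to apply to each site.

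**Conclusion.** The concern does not call for a change. The plan leaves out the words per site, and an analyst working from the Method section would supply them without difficulty: one value from each unit at each of the five blood samples, analysed by area. That gives 250 to 325 pairs per site, above the cited 200 in every case, and 8 complete subjects would be enough.

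A shortfall at every site needs three things that the plan does not say: that five is shared over the sites, that the split is even enough for no site to reach 200, and that 200 applies to each site. The first conflicts with simultaneous recording. Without the third, the study passes on either reading.

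The pair counts under the natural reading assume complete data and nothing else. The precision figures also assume zero bias and r between 0.2 and 0.5, and serve only to show that the stakes are modest. Adding the missing words would do no harm, but it would not alter the design, the data collected or the number of subjects.

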### Medical conditions and criteria of inclusion/exclusion

#### Medical conditions:

13 Healthy subjects

Target population defined in accordance

#### Specific population:

⊠yes □non

Description: among the healthy subjects, at least two must have a dark skin pigmentation as required by 80601-2-61:2011 standard and FDA guidance

#### Inclusion criteria:

- Healthy subject (Man/ Women) > 18 years old
- Subject signed informed consent prior to any screening procedure
- Subject in good health (COHb < 3%, MetHb < 2%, CtHb > 10mg/dL). This criterion is assessed by a finger-prick blood test
- Healthy adult capable of undergoing controlled hypoxemia to the level called for in the protocol with minimal medical risk

Abstract EOXY Page 2 on 4

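### The haemoglobin inclusion limit is printed in mg/dL, which is 0.01 g/dL and excludes nobody

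*Combined protocol and SAP*

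**What the plan says.** The relevant item under Inclusion criteria reads "Subject in good health (COHb < 3%, MetHb < 2%, CtHb > 10mg/dL", and the document adds: "This criterion is assessed by a finger-prick blood test". So total haemoglobin is measured at screening and compared with a fixed number.

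Three other entries could keep out a volunteer with low haemoglobin. None of them gives a haemoglobin value.

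- Inclusion criteria: "Healthy adult capable of undergoing controlled hypoxemia to the level called for in the protocol with minimal medical risk".
- Exclusion criteria: "Subject who would be placed at undue medical risk associated with any procedure called for in the protocol".
- Exclusion criteria: "Subject with blood or skin disorder that may impacting results".

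The Method section describes what subjects then undergo: "The controlled desaturation is performed in five progressive plateaus from 100% to 70"%, the lowest band being 77% to 70%. Five arterial samples are drawn at each plateau. On numbers, it says: "A number of inclusions of 13 was chosen to have at least 10 subjects, in case of drop-outs or analysis exclusions".

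**The concern.** The unit is wrong by a factor that leaves the limit with no function. Total haemoglobin in living adults is measured in whole grams per decilitre, so a floor of 10 mg/dL is met by everyone. A reader who applies the text literally would pass any finger-prick result. A reader who spots the slip has to guess what was meant, because the document gives no second figure to check against.

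What is at stake is a screening safeguard. The sponsor chose to set a numeric floor and to measure it before taking volunteers down to about 70% saturation with repeated arterial sampling. As printed, that part of the check falls back on case-by-case judgement. The accuracy results are not at stake.

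**Working it through.** **Inputs from the document.** Printed limit: above 10 mg/dL (Inclusion criteria). Planned subjects: 13, to secure at least 10 (Method). Samples: 5 at each of 5 plateaus (Method). Pairs of data advised by the ISO standard: 200 (Method). The document gives no derivation of the haemoglobin limit, so there is no calculation of the plan's own to reproduce.

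**Step 1: convert the unit.** 10 mg/dL ÷ 1000 = 0.01 g/dL, or 0.1 g/L.

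**Step 2: test the limit.** The haemoglobin values below are illustrative.

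| Haemoglobin (g/dL) | In mg/dL | Multiple of printed limit | Above 10 mg/dL? | Above 10 g/dL? |
|---|---|---|---|---|
| 3 | 3,000 | 300 | yes | no |
| 7 | 7,000 | 700 | yes | no |
| 9 | 9,000 | 900 | yes | no |
| 10 | 10,000 | 1000 | yes | no |
| 12 | 12,000 | 1200 | yes | yes |
| 15 | 15,000 | 1500 | yes | yes |

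Even 3 g/dL passes the printed limit 300 times over. If 10 g/dL was meant, the printed limit is 10,000 ÷ 10 = 1000 times too low.

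**Step 3: look for a correction elsewhere.** The document contains no other haemoglobin value, no g/dL unit and no anaemia threshold. The COHb and MetHb limits are percentages and do not restrict total haemoglobin.

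**Step 4: size the practical effect.** Let *p* be the proportion of eligible healthy adults at or below 10 g/dL. The document gives no such figure, so I assume a range of 0.001% to 1%. For orientation, assumed normal distributions give:

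- mean 15, SD 1.2 g/dL: *p* = 0.0015%
- mean 13.5, SD 1.2 g/dL: *p* = 0.18%
- mean 13.5, SD 1.5 g/dL: *p* = 0.98%

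Expected exclusions under a 10 g/dL limit are 13 × *p*: from 13 × 0.00001 = 0.00013 to 13 × 0.01 = 0.13.

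The chance of at least one exclusion is 1 − (1 − *p*)^13: from 1 − 0.99999^13 = 0.013% to 1 − 0.99^13 = 12.2%.

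**Step 5: check that the sample size is not touched.** Each subject gives 5 × 5 = 25 pairs per body site. Thirteen subjects give 325 pairs, twelve give 300 and ten give 250. All exceed 200, which needs 200 ÷ 25 = 8 subjects. Losing one volunteer to a corrected limit would not matter.

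**The case against.** The best reply is that this is a one-letter slip which screening staff would query or silently read as g/dL. The text available is a four-page abstract. Its inclusion criteria point to a protocol for the depth of hypoxaemia, which suggests that a fuller protocol exists, and the screening form may carry the right unit. The finger-prick test is done whatever unit is printed, so the investigator applies the medical-risk criteria with a measured value in hand. The prevalence range is assumed and spans three orders of magnitude, and even its upper end implies only 0.13 expected exclusions.

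Most of this stands, and it is why the point is minor. No route from the misprint to actual harm or bias is shown, and an error in the screening form is not shown either. None of it makes the printed limit usable. The limit sits in the eligibility criteria themselves, not in background text, and the document does not say what value should replace it. The blood-disorder exclusion is a weaker backstop than it looks, because it is tied to disorders that may affect the results and not to the subject's safety.

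**Conclusion.** The concern holds as a minor error. The conversion is exact: the printed floor is 0.01 g/dL, and it would exclude 0 of 13 volunteers. Only judgement-based criteria can then turn away someone with low haemoglobin.

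The 1000-fold discrepancy assumes that 10 g/dL was intended, which is very probable but not stated. The 0.013% to 12.2% chance of any exclusion rests on the assumed prevalence range; most likely no volunteer would be affected. The fault is confined to this one limit. The other eligibility criteria, the sample size, the ARMS calculation and the Bland-Altman analysis stand as they are.

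**What to change.** Change the haemoglobin limit under Inclusion criteria to above 10 g/dL, once the sponsor has confirmed that this is the intended value. Make sure the screening form and any fuller protocol carry the same value and unit. Leave the medical-risk and blood-disorder criteria unchanged.

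If subjects have already been screened, compare their recorded finger-prick results with the confirmed limit; for enrolled subjects that is at most 13 values. The correction does not depend on this check.

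The cost is one line of text, with no new procedure and no change to sample size or analysis.

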#### RESUME\_STUDY Clinical study EOXY BIOSERENITY\_80601-2-61

	7
	Exclusion criteria: - Smokers or individuals exposed to high levels of carbon monoxide that result in elevation of carboxy hemoglobin levels
	- Individual subject to conditions that result in elevated levels of methemoglobin
	- Subject who would be placed at undue medical risk associated with any procedure called for in the protocol
	- Subject with open wounds
	- Pregnant woman (negative pregnancy test needed)
	- Subject allergic to silicon, polyamide and silver yarn
	- Subject with cardiorespiratory disorders likely to worsen with thoracic pressure applied by the textile band
	- Subject with mental or motor impairment preventing him from expressing pain
	- Subject with blood or skin disorder that may impacting results
	- Subject with behavioral disorders, too agitated or too aggressive
	- Subject with sensorial disorders, insensible to skin pain
	- Subject susceptible to tension/pressure-based headaches
	No vulnerable subject is enrolled on this study.
Duration of participation and follow-up	Participation duration: 2 days (3 days for subjects of phase 1) No follow-up visit planned
End point criteria	Primary objective: -For performance: Collection of 5 different values of SpO2, SaO2 and HR after each desaturation plateau. These values are used for the analysis of the performance of the EOXY device and the performance of the gold standard, following the ISO 80601-2-61:2011 standardFor safety: Monitoring of vital sign: heart rate ( HR ) continuously, blood pressure and temperature between each desaturation plateau. Also, adverse events are collected during the study.
	Secondary objective 1: FiO2 is assessed to bring subjects near target levels of desaturation plateau. No analysis is performed on these data.
	Secondary objective 2 : Assessment thanks to the signal analysis. No data analysis performed
Statistical method	The clinical performance analysis for this study is assessed by the Accuracy Root-Mean square (ARMs) (calculated by the difference between the investigational pulse oximeter SpO2 measurement and the co-oximeter's SaO2 measurements) and is assessed by the Bland-Altman plot visualizing the difference between SpO2 and SaO2.

Abstract\_EOXY Page 3 on 4

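### With no contact planned after 2 to 3 days of participation, late skin, pressure or catheter-site reactions may be missing from the safety count

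*Combined protocol and SAP*

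**What the plan says.** Under Duration of participation and follow-up, the plan sets participation at 2 days, or 3 for phase 1 subjects, and states "No follow-up visit planned". Phase 1 is not described further.

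Safety is an aim of the study. It is in the title, and the Method section says that the "clinical investigation is conducted in order to assess the performance and safety of pulse oximeters". That section also gives separate assessment of safety at chest, back-torso and forehead as the reason for testing three sites. End point criteria lists safety under the primary objective, as two items:

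- **Vital signs:** heart rate "continuously, blood pressure and temperature between each desaturation plateau".
- **Adverse events:** "adverse events are collected during the study".

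The planned safety analysis, under Safety assessment, is "Assessment of the number of undesirable effects". It has no rate, threshold or hypothesis.

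The exposures, described under Method, are three sensors worn at once and an indwelling arterial catheter. The exclusion criteria screen for some local risks: "Subject allergic to silicon, polyamide and silver yarn", cardiorespiratory disorders that band pressure could worsen, skin disorders, open wounds, reduced ability to feel or express pain, and a tendency to pressure headache.

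**The concern.** The plan treats contact and pressure effects as plausible enough to screen for at entry, and the catheter adds a puncture site. Yet the measurements it schedules (heart rate, blood pressure, temperature) do not detect a local reaction under a sensor or at that site. Such a reaction can enter the safety result only as a reported adverse event, and no planned contact is described once participation ends.

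The whole safety result is a count, so its meaning depends on the window over which events are sought. If some reactions appear after the window closes, a zero at a body area cannot distinguish no reaction from no reaction yet. With 13 subjects, one unrecorded event can change a per-site statement from some to none. A volunteer with a late reaction also has no described occasion on which to be asked about it.

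**Working it through.** **Consistency of the window.** Four statements have to be read together:

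1. Participation lasts 2 days, or 3 for phase 1 subjects.
2. There is no later visit.
3. Adverse events are collected during the study, with no start or end of the period defined.
4. Scheduled safety measurements are tied to the desaturation plateaus.

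The documents do not say on which day the session falls, when sensors and catheter are removed, whether the sites are inspected afterwards, or whether late events can be reported without a visit. The length of observation after removal therefore cannot be derived.

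**The plan's own figures.** It states no expected event rate or count, so there is no safety figure to reproduce. The sample size rests on accuracy data. Each subject gives 5 plateaus × 5 samples = 25 pairs per site, so 10 subjects give 250 and 13 give 325, both above the 200 pairs cited. None of this depends on follow-up.

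**Illustration of the possible loss.** Let n = 13 (Method section), p = per-subject risk of a reaction (assumed), and f = share of reactions that first appear after participation ends (assumed).

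Expected reactions missed = n × p × f:

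| p | f = 0 | f = 25% | f = 50% | f = 75% |
|---|---|---|---|---|
| 5% | 0 | 0.16 | 0.33 | 0.49 |
| 10% | 0 | 0.33 | 0.65 | 0.98 |
| 20% | 0 | 0.65 | 1.30 | 1.95 |

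For example, 13 × 0.10 × 0.50 = 0.65, so the expected recorded count falls from 13 × 0.10 = 1.30 to 0.65.

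Chance of recording at least one reaction = 1 − (1 − p(1 − f))^13. With p = 10%:

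- f = 0: 1 − 0.90^13 = 74.6%
- f = 25%: 1 − 0.925^13 = 63.7%
- f = 50%: 1 − 0.95^13 = 48.7%
- f = 75%: 1 − 0.975^13 = 28.0%

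**What sample size alone contributes.** With 0 events in 13 subjects, the one-sided 95% upper limit is 1 − 0.05^(1/13) = 20.6%; with 10 subjects it is 1 − 0.05^(1/10) = 25.9%. These limits would be the same with complete follow-up, so they do not measure this problem. They show only that a zero count is weak evidence to begin with.

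**The case against.** The strongest reply is that this is a short accuracy study in healthy volunteers, and that omitting a follow-up visit is an explicit choice. The stated aim is "Primary objective: evaluate the SpO2 and HR accuracy of the Bioserenity pulse oximeter (EOXY") and that sentence does not name safety. Adverse events are defined as those collected during the study, so nothing is undercounted against the plan's own definition. The exclusion criteria already remove people at higher risk of local reactions. Ruling out a visit does not rule out a telephone call or spontaneous reporting. The text is a four-page summary, so fuller safety procedures may exist elsewhere.

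Much of this stands. A reader might infer that reactions after sensor and catheter removal are not captured at all, that observation ends on the day of exposure, or that the safety endpoint is shown to be undercounted. The documents support none of these. Session day and removal times are not given, phase 1 subjects have a third day, and some observation after removal is possible. A reader might also divide the 20.6% limit by a capture fraction of one half and say that a zero is compatible with a true rate of about 41%. That fraction has no basis in the documents, and at full capture the limit stays at 20.6%.

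The reply does not remove the gap. Safety is among the primary endpoint criteria and is to be assessed by body area. The exclusions lower the risk without making it nil. Unplanned reporting is also not the same as asking every subject the same questions at a fixed time.

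**Conclusion.** The concern holds in a limited form. Reactions that first appear after the 2 to 3 days of participation may be missed, and the count of undesirable effects may be too low. The direction of any error follows from the design; its size cannot be computed, because the documents give neither a reaction risk nor a share appearing late. At an assumed 10% risk in 13 subjects, the expected loss runs from 0 (none late) to 0.98 reactions (75% late). That some reactions appear late is itself an assumption, and if none do, nothing is lost.

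The root-mean-square accuracy and Bland-Altman analyses are unaffected. This is an inexpensive improvement to the safety part of the study, and no accuracy conclusion depends on it.

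**What to change.** Keep the decision not to hold a follow-up visit, and add one remote contact (telephone or message) some days after the session. Use fixed questions on the skin at each of the three sensor sites, the catheter site and headache. Define the adverse event period as running from a stated start to that contact, and report the count by site over that period.

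If the contact is not added, state the adverse event period explicitly and limit the per-site safety conclusion to effects seen during the 2 to 3 days of participation.

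The first option costs one short contact for each of 13 subjects by existing staff, a line in the consent form and the data form, and a few days' delay to last data. It adds no visit or procedure. The second costs only wording.

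### Device safety is to be assessed separately on chest, back-torso and forehead, but the plan describes no safety measurement or tabulation by site

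*Combined protocol and SAP*

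**What the plan says.** The aim is in the Method section: "Different body areas are tested in order to assess separately the safety and performance of the EOXY device on these areas". The same section gives the layout: "Three EOXY pulse oximeters record the SpO2 and HR at the same time in 3 different body areas: chest, back-torso, forehead". Saturation is lowered in five steps to 70%, with an arterial catheter in place.

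End point criteria places safety under the primary objective. Heart rate is followed "continuously, blood pressure and temperature between each desaturation plateau. Also, adverse events are collected during the study". The Safety assessment row gives the only summary: "Assessment of the number of undesirable effects".

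The Exclusion criteria point to local concerns: "Subject allergic to silicon, polyamide and silver yarn", "Subject with sensorial disorders, insensible to skin pain" and "Subject susceptible to tension/pressure-based headaches". They also bar people with open wounds, people whose impairment would stop them expressing pain, and people with cardiorespiratory disorders that band pressure on the thorax might worsen. The row on duration states that there is no follow-up visit.

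**The concern.** A safety aim stated for each body area needs at least one safety measure recorded for each body area. The plan describes none. What it schedules is systemic, and what it summarises is a single count.

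The study could therefore report few or no undesirable effects without anyone having inspected the skin under a sensor, and a reader could not tell whether forehead, chest and back differ. A statement that the device is safe on each site would then rest on a measurement that the plan does not describe. The exclusions suggest that the sponsor already had skin contact, pain and pressure in mind, so the missing measures are foreseeable ones.

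**Working it through.** The plan states no numerical safety target, so there is no figure to reproduce. The check sets the aim against the measurements.

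**1. Can the scheduled measurements speak to a site?**

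- Heart rate, blood pressure and temperature each give one value per subject at a time, while three sensors are worn. Three sites cannot be distinguished from one shared value.
- All three are taken within the desaturation session. No period without sensors is described for comparison, so a sensor effect and a procedure effect cannot be separated.

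**2. Can the adverse event data speak to a site?** Possibly, if site is recorded. End point criteria gives no method of elicitation, timing or body site. Safety assessment gives a number, with no breakdown by site and no grade.

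**3. Are the local concerns measured?**

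| Concern suggested by the exclusions | Local measure described |
|---|---|
| Contact allergy, open wounds | None |
| Skin pain | None |
| Pressure headache | None |
| Band pressure on the thorax | None (heart rate or blood pressure might react, but not separably) |

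**4. Scale.** 13 subjects x 3 sites = 39 placements, or 10 x 3 = 30 if only the minimum of 10 subjects remains. This takes one placement per site per subject; the extra day for phase 1 subjects could add more. Local examinations described: 0.

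**5. What a count of zero would mean.** With n subjects at a site, no reactions and complete detection, the one-sided 95% upper bound on the reaction rate is 1 − 0.05^(1/n):

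- n = 13: 1 − 0.05^(1/13) = 20.6%
- n = 10: 1 − 0.05^(1/10) = 25.9%

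If only a fraction s of reactions is detected, the bound applies to s times the true rate. At an assumed s = 0.5 and n = 13, the bound on the true rate is 20.6% / 0.5 = 41.2%. With s unknown, a count of zero cannot be interpreted.

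**6. Chance of seeing at least one reaction at a site**, 1 − (1 − p·s)^n. The documents give neither p (true rate per subject at that site) nor s; both are assumptions, shown over a range:

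| n | p | s = 0.25 | s = 0.50 | s = 0.75 | s = 1 |
|---|---|---|---|---|---|
| 13 | 10% | 28% | 49% | 64% | 75% |
| 13 | 20% | 49% | 75% | 88% | 95% |
| 10 | 10% | 22% | 40% | 54% | 65% |
| 10 | 20% | 40% | 65% | 80% | 89% |

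The direction does not depend on the values chosen: at this sample size, incomplete detection lowers the chance of seeing anything at all.

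**The case against.** The best defence is that the stated safety outcome is a count of undesirable effects, not an analysis of vital signs. The plan already calls the vital signs monitoring. A local reaction, once noted, can usually be located by where it occurs. The two pain-related exclusions help to ensure that enrolled subjects can feel and report a problem. The document is a four-page summary that refers to procedures called for in a protocol, so removal checks and adverse event procedures may be written elsewhere. Finally, the statistical method concerns accuracy only, which a skin check does not change.

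Much of this stands, and it rules out several stronger readings that a reader might infer:

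- *The vital signs respond to the hypoxia and not to the sensor.* The documents do not say so. They do not state that temperature reacts to desaturation, and the exclusion on thoracic pressure leaves room for a band effect on heart rate or blood pressure. What holds is that no such effect could be separated or located.
- *Local effects are never examined, or are caught only if someone volunteers them.* The text is silent on how events are elicited. It supports only that no examination or question is described.
- *A rise in heart rate under desaturation would count against the device.* No threshold or comparison makes heart rate a device-safety result.

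The defence does not supply a per-site measure. A count with no stated elicitation, grade or site does not answer an aim stated by site, and relying on subjects to report pain does not cover painless redness or marks.

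**Conclusion.** The point holds in this form: as written, the plan does not support its own aim of assessing safety separately on the three body areas. The scheduled measurements are systemic and confounded with the procedure. The event count has no described elicitation or site. No local check is described for 39 planned placements, and there is no follow-up visit at which a delayed reaction might be seen.

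This rests on the available summary; a fuller protocol that described local checks would answer it. Treating the exclusions as a guide to foreseeable local effects is an inference, though a natural one. No expected number of missed reactions can be given, because the documents contain no reaction or reporting rate. SpO2 and heart rate accuracy and the number of subjects are not affected.

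**What to change.** Add to the safety endpoint:

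- A scripted check of the skin under each of the three sensors, before placement and at removal, on a fixed grade: none, redness, mark or indentation, lesion.
- One fixed question on pain at each site and one on headache.
- A table of these findings and of all adverse events by body site, with the number of placements examined as denominator.
- A sentence describing heart rate, blood pressure and temperature as monitoring of the desaturation procedure.

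The check before placement lets existing marks be told apart from new ones. If a local check already exists in another study document, it is enough to state it here and add the table by site.

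The cost, by estimate, is a few minutes per subject for staff who already place and remove the sensors, plus one more case report form page. More mild reactions will be counted, so the safety result may look less favourable than under the present wording. No change to the sample size or the desaturation schedule is needed.
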